### **12.5.2 Definition of a Serious Adverse Event**

Any AE that fulfills any one of the criteria listed below must be recorded as an SAE. An SAE is described as any untoward medical occurrence that at any dose:

Results in death

Is life-threatening

Requires hospitalization or prolongation of hospitalizationb

Hospitalization does not necessarily include the following:

- Rehabilitation/hospice/nursing facility
- Emergency Room/Department visit less than 24 hours
- Elective or preplanned admission/surgery/Day surgery
- Protocol-specified admission
- Admission for a pre-existing condition not associated with either a new AE or with worsening of a pre-existing AE

Results in persistent or significant disability/incapacity

Is a congenital anomaly/birth defect

Is an important medical eventc

- a. The term "life-threatening" in the definition of "serious" refers to an event in which the patient was at risk of death at the time of the event; it does not refer to an event which hypothetically might have caused death if it were more severe.
- b. Hospitalization requires inpatient or prolongation of an existing hospitalization. AEs that are associated with hospitalization or prolongation of hospitalization are considered SAEs.
- c. Important Medical Event: Medical and scientific judgment should be exercised in deciding whether expedited reporting is appropriate in other situations, such as important medical events that may not be immediately life-threatening or result in death or hospitalization but may jeopardize the patient or may require intervention to prevent one of the other outcomes listed in the definition above. These should also usually be considered serious. Examples of such events are intensive treatment in an emergency room or at home for allergic bronchospasm; blood dyscrasias or convulsions that do not result in hospitalization; or development of drug dependency.

Severity and seriousness must be differentiated. Severity describes the intensity of an AE while the term seriousness refers to an AE that has met the criteria for an SAE as described above.

### 12.5.3 Severity Assessment

An assessment of severity will be made by the Investigator using the following criteria:

- Mild: events require minimal or no treatment and do not interfere with the patient's daily activities.
- Moderate: events result in a low level of inconvenience or concerns with the therapeutic measures. Moderate events may cause some interference with functioning.
- Severe: events interrupt a patient's usual daily activity and may require systemic drug therapy or other treatment. Severe events are usually incapacitating.

Change in severity of an AE should be documented based on specific guidance in the eCRF Completion Guidelines.

Severity and seriousness must be differentiated: severity describes the intensity of an AE while seriousness refers to an AE that has met the criteria for an SAE.

### 12.5.4 Causality Assessment

An Investigator causality assessment must be provided for all AEs (both nonserious and serious). This assessment must be recorded on the CRF/eCRF and any additional forms as appropriate.

The definitions for the causality assessments are as follows:

- Not related (unrelated): This relationship suggests that there is no association between the study drug and the reported event.
- Unlikely related: This relationship suggests that the clinical picture is highly consistent with a cause other than the study drug, but attribution cannot be made with absolute certainty and a relationship between the study drug and AE cannot be excluded with complete confidence.
- Possibly related: This relationship suggests that treatment with the study drug may have caused or contributed to the AE, ie, the event follows a reasonable

temporal sequence from the time of drug administration and/or follows a known response pattern to the study drug but could also have been produced by other factors.

- Probably related: This relationship suggests that a reasonable temporal sequence of the event with the study drug administration exists and the likely association of the event with the study drug. This will be based upon the known pharmacological action of the study drug, known or previously reported adverse reactions to the study drug or class of drugs, or judgment based on the Principal Investigator's clinical experience.
- Definitely related: Temporal relationship to the study drug. Other conditions (concurrent illness, concurrent medication reaction, or progression/expression of disease state) do not appear to explain event, corresponds with the known pharmaceutical profile, improvement on discontinuation, re-appearance on re- challenge.

### 12.5.5 Outcome

For all AEs, regardless of causal relationships, the Investigator must follow-up on the outcome of the event until the event or sequelae either resolves or stabilizes.

If a patient experiences a SAE with an outcome of death:

- The SAE resulting in death should have an outcome documented as death/fatal with an end date being the date of death.
- If the patient had additional AEs/SAEs that were ongoing at the time of death, these events would be documented as ongoing with no end date.
- Only 1 event should have an outcome of death/fatal unless an autopsy report or Investigator states otherwise.

### 12.5.6 Recording Adverse Events

All observed or volunteered AEs regardless of causal relationship must be reported as described in [Section 12.5.4](#).

For all AEs, the Investigator must obtain adequate information for the following:

1. determine the outcome of the AE;
2. determine if the event meets criteria for an SAE;
3. assess the severity of the AE;
4. determine the causality of the AE.

Adverse events must be documented in clear, unambiguous medical term. Study personnel are advised not to use abbreviations or acronyms.

For each AE, record only the diagnosis on the AE page of the CRF/eCRF. Do not report the characteristic signs and symptoms of the diagnosis as additional AEs.

If a diagnosis is not available, record each sign and symptom as an AE. When a diagnosis becomes available, study personnel are to update the source document and the AE page of the CRF/eCRF with relevant diagnosis only.

For medical or surgical procedures (eg, surgery, endoscopies, tooth extraction, transfusion), the condition/diagnosis that leads to the procedure should be recorded as the AE (eg, laparoscopic cholecystectomy is the procedure or treatment for an SAE of necrotic gall bladder).

All AEs that later increase in the frequency and/or severity (medical and scientific judgment should be exercised by the Investigator) will be considered new AEs and will be recorded on a new line in source and the CRF/eCRF.

Withdrawal due to an AE or SAE must be clearly differentiated from withdrawal due to other reasons.

### **12.5.7 Reporting of Serious Adverse Events to Sponsor**

All AEs must be assessed by the Investigator to determine if they meet criteria for an SAE. All SAEs must be reported to the Sponsor or designee immediately or within 24 hours of the Investigator or their staff becoming aware of them regardless of the presumed relationship to the study drug.

The Investigator must complete, sign, and date the SAE pages, verify the accuracy of the information recorded on the SAE pages with the corresponding source documents, and send a copy via email or fax to the contact information provided [REDACTED]

When further information becomes available, the SAE Form should be updated with the new information and reported immediately via the same contact information.

Additional follow-up information, if required or available, should be entered into the CRF/eCRF and sent to the Sponsor within 24 hours of the Investigator site or their staff becoming aware of this additional information via the reporting process outlined above. These reporting timelines need to be followed for all initial SAE cases and follow-up versions of the initial cases.

For all SAEs the Investigator must provide the following:

- Clear identification of the Investigator/Reporter with full contact information, country and site number
- Subject identification details (subject's unique study identification number)
- Investigational Medicinal Product(s) administration details (dose and dates) Seriousness criteria
- Appropriate and requested follow-up information in the time frame detailed above
- Causality of the serious events
- Outcome of the serious events
- Medical records and laboratory / diagnostic information

### **12.5.8 Reporting Requirements**

This protocol will use the current IB as the Reference Safety Document. The expectedness and reporting criteria of an SAE will be determined by the Sponsor from the Reference Safety Document.

#### **12.5.8.1 Sponsor Reporting Requirements**

The Sponsor or its legal representative is responsible for notifying the relevant regulatory authorities of SAEs meeting the reporting criteria.

---

**12.5.8.2 Investigator Reporting Requirements**

The Investigator must fulfill all local regulatory obligations required for the study Investigators. It is the PI's responsibility to notify the IRB or Independent Ethics Committee (IEC) of all SAEs that occur at his or her site. Investigators will also be notified of all unexpected, serious, drug--related events (7/15 Day Safety Reports) that occur during the clinical study. Each site is responsible for notifying its IRB or IEC (if local) of these additional SAEs. Investigators will receive blinded information unless unblinded information is judged necessary for safety reasons.

## **13 STATISTICAL METHODS AND PLANNED ANALYSES**

### **13.1 General Considerations**

Data collected during the study will be presented in summary tables, figures, or by-patient data listings. Continuous variables will be summarized using mean, standard deviation (SD), median, minimum, and maximum. Categorical variables will be summarized using percentages and frequency distributions. No formal hypothesis testing will be performed.

### **13.2 Determination of Sample Size**

At least 4 MoCD Type A patients will be enrolled in the study. The actual sample size will depend on the number of eligible patients currently being treated with rcPMP.

### **13.3 Analysis Population**

Efficacy analyses will be performed on the Full Analysis Set (FAS). Due to the small number of patients, a Per-Protocol Population will not be utilized for this study. The FAS will include all patients who receive at least 1 dose of ORGN001.

Safety analyses will be performed on the Safety Set, defined as all patients who receive at least 1 dose of ORGN001.

### **13.4 Demographics and Baseline Characteristics**

All demographic and baseline characteristics information will be summarized for all patients. For categorical variables, frequencies and percentages will be presented. Continuous variables will be summarized using descriptive statistics (mean, median, SD, and minimum and maximum).

### **13.5 Patient Disposition and Treatment Compliance**

The number of patients screened, treated, completing the 6-Month Initial Treatment Period, and included in the safety and efficacy analysis sets will be tabulated by counts and percentage of patients. Reasons for any patient withdrawals will be provided.

Treatment compliance with ORGN001 will be presented for all patients.

### **13.6 Prior and Concomitant Medications**

Prior and concomitant medications will be summarized using the Safety Set. Listings of prior and concomitant medications will be produced as will listings of seizure medications.

Medications will be coded using the World Health Organization Drug Dictionary (WHODrug) version 01 September 2013 or higher. Medication summaries will be presented by WHODrug Anatomical Therapeutic Chemical (ATC) and by WHODrug generic name.

### **13.7 Efficacy Analyses**

Efficacy analyses will be performed on the FAS.

#### **13.7.1 Primary Efficacy Analysis**

There is no prespecified primary efficacy endpoint in this study. Secondary efficacy analyses are described in [Section 13.7.2](#) [REDACTED].

### 13.7.2 Secondary Efficacy Analyses

The secondary efficacy endpoints include:

- Change from baseline in urine and blood SSC levels
- Change from baseline in clinical findings from neurologic examination
- Change from baseline in age-appropriate motor and cognitive assessments (Bayley--III, GMFCS, WPPSI)
- Change from baseline in seizure frequency
- Change from baseline in neuroimaging
- Changes in growth parameters (body weight, body length, head circumference)
- Change from baseline in feeding patterns

Baseline is defined as the last available assessment prior to treatment with ORGN001 except for blood and urine biomarkers whereby baseline is defined as the average of all available assessments prior to treatment with ORGN001.

Observed urine and blood SSC levels as well as changes and percentage changes from baseline to the study time points will be summarized. Individual patient plots over time will be produced.

Shifts from baseline in clinical findings from neurologic examination and neuroimaging findings will be presented for the different time points. The frequency of seizures will be summarized.

Observed values and changes in GMFCS, WPPSI, and Bayley-III cognitive, language, and gross and fine motor scores will be summarized.

Growth parameters (weight [kg], length [cm], and head circumference [cm]) will be converted to age-adjusted z-scores and descriptive statistics will be presented for each parameter over time. In addition, the following individual patient's growth charts will be produced as specified in the statistical analysis plan (SAP) with a flag for start of ORGN001 infusion: Weight-for-age percentiles, length-for-age percentiles and head circumference-for-age-percentiles.

### 13.8 Safety Analyses

Safety analyses will be performed on the Safety Set defined as all patients who receive at least 1 dose of ORGN001.

#### 13.8.1 Adverse Events

All AEs will be coded using the Medical Dictionary for Regulatory Activities (MedDRA) (version 15.1 or higher).

Adverse events occurring from the signing of informed consent and prior to the initiation of study drug treatment (pretreatment AEs) will be summarized.

Treatment-emergent AEs are AEs that begin after the start of ORGN001. Treatment-emergent AEs will be summarized by incidence, Preferred Term, System Organ Class (SOC), seriousness, severity, relationship to treatment.

All AEs will be summarized by both event counts and patient counts. For patient counts, if a patient has more than one occurrence of an AE for a specific Preferred Term or SOC, the patient will be counted only once for that Preferred Term or SOC. The most severe occurrence of an AE as well as the most extreme relationship of the AE will be indicated in cases of multiple occurrences of the same AE at onset of the AE.

### **13.8.2 Laboratory Parameters**

Changes from Baseline in laboratory assessments (chemistry and hematology) will be summarized by visit, and shift tables (L [low], N [normal], H [high]) by visit will be produced for clinical laboratory tests.

### **13.8.3 Physical Examinations and Vital Signs**

Physical examinations and Child-Pugh scores (A [a score of 5 to 6], B [a score of 7 to 9], C [a score of 10 or above]) will be summarized by visit. Vital signs (systolic and diastolic BP, temperature, heart rate, and respiratory rate) and changes from baseline in vital signs will be summarized by visit.

### **13.8.4 Electroencephalograms**

The number and percentage of patients with EEG findings will be summarized by visit.

## **13.9 Pharmacokinetic Analysis**

Plasma concentration versus time profiles will be graphically summarized. Non-compartmental PK parameters such as  $C_{max}$ ,  $t_{max}$ , AUC, and  $t_{1/2}$  will be determined if possible, and dose linearity will be explored. Plasma concentration and PK parameter summaries will include descriptive statistics, as appropriate. Details of PK analyses will be presented in an analysis plan.

## **13.10 Other Statistical Issues**

### **13.10.1 Missing or Invalid Data**

If a date of a measurement or an event has a missing or an unknown day, the missing or unknown Day will be substituted by 15 for the calculation of other variables such as age at which the measurement was taken, or the age at the occurrence of an event. If the month or the year of a date is missing, no imputation will take place. In general, other missing or invalid observations will not be replaced or imputed unless otherwise specified in the SAP.

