3.1. Changes from Analyses Specified in the Protocol

Not applicable.

[REDACTED]

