6.1.3.2. Disease Characteristics

The following disease characteristics will be summarized:

- Age at onset of first MoCD signs/symptoms (days)
- Age at genetic diagnosis (days)
- MoCD Presenting signs and symptoms

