6.2.1.1. Handling of Dropouts or Missing Data

In general, missing or invalid observations will not be replaced or imputed. The following imputation rules apply to partially missing start and end dates:

- Any imputed dates need to be logical.
- Imputation of start date:
 - Missing day and month:
 - If partial date year < year of the first dose date, then impute December 31.
 - If partial date year = year of the first dose date, then impute to first dose date.
 - If partial date year > year of the first dose date, then impute to January 1.
 - Missing day only:
 - If the partial month and year < month and year of the first dose date, then impute last day of the start date month.
 - If the partial month and year = month and year of the first dose date, then impute the day of first dose.
 - If the partial month and year > month and year of the first dose date, then impute first day of the start date month.
 - If the imputed start date is after the stop date, the start date will be imputed to be equal to the stop date.
- Imputation of end date:
 - Missing day and month:
 - If partial date year < year of the last dose date, then impute December 31.
 - If partial date year = year of the last dose date, then impute to last dose date.
 - If partial date year > year of the last dose date, then impute to January 1.
 - If partial date has missing day only:
 - If the partial month and year < month and year of the last dose date, then impute last day of the start date month.
 - If the partial month and year = month and year of the last dose date, then impute the day of last dose.

- If the partial month and year > month and year of the last dose date, then impute first day of the start date month.
- If the imputed stop date is before the start date, the stop date will be imputed to be equal to the start date.

For subjects continuing treatment at time of analysis, the data cut-off will be used.

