8. APPENDICES

8.3. Technical Specifications for Derived Variables

The following derived data will be calculated prior to analysis.

Age

Age will be presented as the number of days or months between date of birth and the reference date and will be calculated as follows:

Age in days: (Visit date – date of birth) + 1 day

Age in months: ((Visit date – date of birth) + 1 day)/30.4375

The following ages in [Table 3](#) may be computed, with reference dates indicated.

Table 3: Age and Reference Date

AGE	REFERENCE DATE
Age at study enrollment (months)	• Date of signing ICF
Age at first symptom (days)	• Date of first symptoms
Age at first ORGN001 infusion (days)	• Date of first infusion
Age at each developmental assessment (months)	• Date of developmental assessment

If the reference date is not complete, then age at reference date will be determined by the month and/or year of date of birth and reference date.

Weight and Height

Weight in pounds will be multiplied by 0.4536 to be converted to kilograms; and height in inches will be multiplied by 2.54 to be converted to centimeters.

The BMI will be calculated by dividing the subject's weight in kilograms by the subject's height in meters squared. The units are kg/m².

BQL and LLOQ Values for Clinical Laboratory Parameters

For all clinical laboratory parameters, values that are reported as below quantification level (BQL) or lower limit of quantification (LLOQ) will have numeric values set equal to the BQL or LLOQ lower limit (e.g., if BQL <2, then value will be set equal to 2). However, the original value will be displayed in by-subject data listings.

Date of Infusion

Date of first ORGN001 infusion, as well as date of last ORGN001 infusion will be derived.

Time from First Infusion to Applicable Assessments (Days)

For all applicable assessments, time on treatment from first infusion will be calculated as follows:

- If visit date is on or after first infusion = (Visit date – Day 1 Infusion date) + 1 day
- If visit date is prior to first infusion = (Visit date – Day 1 Infusion date)

Time from First Infusion to Applicable Assessment (Months)

For all applicable assessments, time on treatment from first infusion will be calculated as follows:

- If visit date is on or after Day 1 infusion = ((Visit date – Day 1 Infusion date) + 1 day)/30.4, rounded to 1 decimal place
- If visit date is prior to Day 1 infusion = (Visit date – Day 1 infusion date)/30.4, rounded to 1 decimal place

Time on Study (Days)

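### The protocol and SAP treat partial dates differently without declaring it, and the protocol's day-15 rule can date first symptoms before birth

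*Protocol*

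**What the plan says.** Protocol 13.10.1 covers the date of a measurement or event. With the day unknown, "the missing or unknown Day will be substituted by 15 for the calculation of other variables such as age"; both examples it gives are ages. For anything less complete: "If the month or the year of a date is missing, no imputation will take place". It hands over to the SAP only for the remainder: "other missing or invalid observations will not be replaced or imputed unless otherwise specified in the SAP". Dates have already been dealt with by then, so the handover does not reach them.

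The SAP has three other rules that could touch an onset date:

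- **SAP 8.3 (ages).** With an incomplete reference date, "then age at reference date will be determined by the month and/or year of date of birth and reference date". Table 3 in that section includes age at first symptom, in days. No formula is given for the incomplete case.
- **SAP 6.2.1.1 (partial start and end dates in general).** For a start date before the first-dose month: "If the partial month and year < month and year of the first dose date, then impute last day of the start date month". For the same month: "If the partial month and year = month and year of the first dose date, then impute the day of first dose". For a later month it uses the first day. It also fills in a missing month, with 31 December, the first dose date or 1 January.
- **SAP 6.2.1.1.2 (medical history and prior medications).** A missing start day becomes the first of the month, and a missing day and month become 1 January.

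Day 15 is not used in the readable SAP. The readable entry in SAP 3.1, where departures from the protocol belong, is "Not applicable"; a redacted block follows it. SAP 6.1.3.2 plans to summarize "Age at onset of first MoCD signs/symptoms (days" and age at genetic diagnosis, both in days.

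**The concern.** Protocol 1.3 describes a disease that presents within hours or days of birth, so onset will usually fall in the birth month. An arbitrary day in that month can miss by more than the age being measured, and day 15 can give an onset date before the child was born. Partial onset dates are plausible: Protocol 8.2 asks for them only where they can be obtained, and they are collected in retrospect from children already on rcPMP.

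The plan calls for at least 4 patients, so one badly imputed value can dominate the mean and the range. Since no change is declared, a programmer following the protocol and one following the SAP would each be within a governing document and would report different ages.

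**Working it through.** The plan gives no figure to reproduce. The check applies each rule to the same dates.

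**Formula.** SAP 8.3: age in days = (date − date of birth) + 1. Onset on the day of birth is age 1; an age below 1 means onset before birth.

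**When day 15 precedes birth.** Let b be the day of birth and let onset fall in the birth month. Imputed age = 15 − b + 1 = 16 − b, which is 0 or less for every b of 16 or more. That is 13 of 28, 15 of 30 or 16 of 31 possible birth days.

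**Illustrative grid (assumption).** A 30-day month, b = 1 to 30, true onset 0 to 3 days after birth and within the month, onset day missing.

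- Combinations: birth days 1–27 give 4 each, and days 28, 29 and 30 give 3, 2 and 1. 27 × 4 + 6 = 114.
- True mean age: (27 × 10 + 6 + 3 + 1)/114 = 280/114 = 2.46 days.
- Born on day 16 or later: 12 × 4 + 6 = 54, so 54/114 = 47% get onset before birth under day 15.
- Onset falls on days 1, 2 and 3 in 1, 2 and 3 combinations, and on each of days 4–30 in 4. The absolute error of day 15 is then (14 + 26 + 36 + 264 + 480)/114 = 820/114 = 7.2 days on average.

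| Rule | Error in days | Mean absolute error |
|---|---|---|
| Protocol 13.10.1, day 15 | −15 to +14 | 7.2 |
| SAP 6.2.1.1, last day (only if it governs onset) | 0 to +29 | 1570/114 = 13.8 |
| SAP 8.3, same month read as age 0 | −4 to −1 | 280/114 = 2.5 |
| Onset set to date of birth (age 1) | −3 to 0 | 166/114 = 1.5 |

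**One child under each rule.** Born on the 10th of a 31-day month, onset that month, day missing: 15 − 10 + 1 = 6 days (Protocol 13.10.1); 31 − 10 + 1 = 22 days (SAP 6.2.1.1); 1 − 10 + 1 = −8 days (SAP 6.2.1.1.2, if onset is handled as medical history).

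**Month missing.** Born 20 March 2013, onset known only as 2013, first dose in 2014. The protocol imputes nothing. SAP 6.2.1.1 uses 31 December, giving 287 days. SAP 6.2.1.1.2 uses 1 January, giving −77 days.

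**Effect on the summary.** With 4 patients, a single day-15 error of −15 days moves the mean by 15/4 = 3.75 days, more than the true mean of 2.46 on the grid.

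**The case against.** **The SAP is the more specific document, and its age rule is tolerable.** A reader might infer that no stated rule works. That goes too far. SAP 8.3 is written for ages, and if same-month onset is read as age 0 it errs by only 1 to 4 days on the grid. SAP 6.2.1.1 also requires imputed dates to be logical, which rules out onset before birth within the SAP. What remains is that SAP 8.3 states no formula, the SAP does not say which of its sections governs onset, and the departure from the protocol is not declared.

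**The last-day figure may not apply.** One might conclude that the SAP overstates age by about 14 days. SAP 6.2.1.1 is built around start and end dates relative to dosing, and ages have their own rule, so the documents do not establish this.

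**Treatment-emergent status.** A reader might infer that the two documents classify the same adverse event differently and so disturb the primary safety objective. If day 15 were applied, an event in the first-dose month with no day would be pre-treatment whenever first dose fell on day 16 or later (13 of 28 to 16 of 31 days). But the protocol names only ages as examples and has no partial-date rule for treatment emergence; the conflict follows only from its general wording. SAP 6.2.1.1.4, 6.5.3 and 8.3 settle the matter conservatively: the event counts as treatment-emergent unless it can be shown to precede first dose. Adverse events are also collected prospectively, with daily review in the first 2 weeks (Protocol 3.4), so a missing day just after first dose is unlikely. No safety result needs to change.

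**Small consequence.** Age at onset is not an endpoint, no decision rule uses it, and no hypothesis is tested. This stands and limits the weight of the point.

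**Conclusion.** The inconsistency is explicit for ages at events, and on the readable text it is undeclared. The protocol's rule is also unsuitable for age at first symptoms, because it produces impossible values for about half of possible birth days when onset is in the birth month. The 47% depends on the assumed 30-day month and onset within 3 days, and on the day being missing; how often that happens is not stated. The effect is confined to descriptive disease characteristics in a very small study. It does not reach the safety or efficacy endpoints. It is worth correcting because a stated rule gives a wrong value and the correction is cheap.

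**What to change.** In the SAP:

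1. Name one partial-date rule for ages at onset and at genetic diagnosis, in SAP 8.3, that never places the event before the date of birth. One example is the later of the date of birth and the first of the known month. On the grid this equals the date-of-birth rule (mean absolute error 1.5 days). Say also what happens when the month is missing; leaving the age missing would keep to the protocol.
2. Flag imputed values in the by-subject listing.
3. In SAP 3.1, list the departure from Protocol 13.10.1, and state that for adverse events the existing SAP rule applies instead of day 15.

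A midpoint rule is not needed: on the same grid the midpoint between birth and month end has a mean absolute error of 6.2 days. Nor is a second summary without imputed values, given the listings.

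The cost is a few lines of SAP text and no new data. Keeping the change in the SAP avoids a protocol amendment and the ethics re-approval that Protocol 16.1 attaches to one.
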